# **30.2.3** Longitudinal Modeling for Effectiveness

For effectiveness, the time-to-failure during the 9-month(39 weeks) post-blanking period is modeled by using a piecewise exponential model. The model has three distinct time intervals: (0, 2], (2, 8], and (8, 39] weeks. Failure times during each interval is exponentially distributed, with different hazard rates in each segment. The model is:

$$f(t) = \exp(-th(t)),$$

$$h(t) = \begin{cases} h_1 & 0 < t \le 2; \\ h_2 & 2 < t \le 8; \\ h_3 & 8 < t \le 39. \end{cases}$$

These intervals are based on a model used in the ThermoCool Pivotal trial. A vague Gamma(1, 1) prior distribution will be used for each h in the model.

Given hazard rates  $h_1, h_2$ , and  $h_3$ , the failure-free rate at 12 months  $p_E$  can then be estimated by

 $p_E = \exp(-[2h_1 + (8-2)h_2 + (39-8)h_3]).$ 

At the interim, the total number of primary effectiveness events and the total subject exposure time will be used to update the vague Gamma prior and obtain the posterior Gamma distribution for each segment. Then 10,000 random hazard rates will be sampled from the posterior distribution for each segment and each triplet set of hazard rates will be used to calculate  $p_E$ . The distribution of  $p_E$  is estimated based on the 10,000 calculated  $p_E s$ . If the probability of  $p_E$  being greater than 50% is greater than 0.9975(99.75%), the trial will declare early success.

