# 18.9.6 Plans for Interim Analysis

One (1) interim analysis per arm is planned for early success claim in the Main study. The details on the timing of the interim analysis are provided in the simulation report and the SAP. For the safety endpoint, the outcome for all patients will be known at the time of the interim analysis in each arm, and therefore, the primary safety analyses will be performed at the time of the interim analyses. Early success will be declared at the interim analysis for the Main study if:

- 1. The safety objective has already been met, and
- 2. Posterior probability of the effectiveness proportion  $p_E$  being greater than 50% is greater than 0.9975

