# **30.0 APPENDIX D ADAPTIVE DESIGN MAIN STUDY**

# Simulation Report for Q-FFICIENCY Study Main Study

### **30.1** Introduction

This document describes the single-arm trial design for Biosense Webster's pre-market clinical evaluation of the QDOT MICROTM Catheter to demonstrate the acute safety and 12-months effectiveness. The trial will enroll N=185 subjects. One interim analysis for early success will be performed at 6 months after the last patient is enrolled.

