### **30.2.2** Interim Analyses for Early Success

One interim analysis is planned for an early success claim. The interim will occur 6 months after enrollment is complete; that is, 6 months before the final analysis. For the safety endpoint, the outcome for all patients will be known at the time of the interim analysis and therefore the primary safety analysis will be performed at the time of the interim analysis. It should be noted that because these two tests are identical there will not be an increase in type-I error.

At the interim analysis, the trial will declare early success if:

1. The safety objective is met.

Biosense Webster, IncVersion 5.0 – Feb 3, 2021CONFIDENTIAL

2. Posterior probability of the effectiveness proportion  $p_E$  being greater than 50% is greater than 0.9975.

3. .

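### Judging a 0.9975 cut-off from 10,000 posterior draws makes the interim effectiveness decision depend on the random seed in about 2–3% of trials near the design assumption, with almost no effect on overall success

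*Protocol*

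**What the plan says.** The early-success rule appears in Protocol section 18.9.6, where the safety objective must be met and the posterior probability of the effectiveness proportion "being greater than 50% is greater than 0.9975". Section 30.2.2 repeats it.

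Section 30.2.3 says how that probability is obtained. Each of three hazards gets a gamma posterior. "Then 10,000 random hazard rates will be sampled from the posterior distribution for each segment"; each triplet is converted to a failure-free rate, and the distribution of that rate "is estimated based on the 10,000 calculated" values. If the resulting probability "is greater than 0.9975(99.75%), the trial will declare early success". The number of draws is therefore part of the pre-specified decision rule, not only a setting of the design simulations.

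The documents in hand give no random seed, no tolerance for Monte Carlo error, no rule for a borderline result and no exact calculation. The SAP supplied covers only the Variable Flow study, which has no such interim. The Main-study SAP is not among the documents.

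**The concern.** An interim decision should follow from the data. Here the quantity compared with the cut-off is itself a random estimate, and the cut-off lies far in the tail, where few draws carry the information. When the exact posterior probability is close to 0.9975, one correct run can declare early success and another can decline it on identical data.

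The interim is not a side route. Section 30.4.2 reports that 64.8% of simulated trials claim success there at the planning rates, out of 81.7% overall. Under sections 18.4.1 and 18.9.4, once early success is declared the full 12-month effectiveness data are only summarised. If it is not declared, they are formally tested. A borderline seed therefore decides the timing of the claim and the status of the 12-month result.

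**Working it through.** **Inputs (Protocol).**
- Size and look: "The trial will enroll N=185 subjects" (30.1); "The interim will occur 6 months after enrollment is complete" (30.2.2).
- Model: "The model has three distinct time intervals: (0, 2], (2, 8], and (8, 39] weeks"; "A vague Gamma(1, 1) prior distribution will be used for each h in the model" (30.2.3).
- Hazards for simulation (30.3.1): h1 = 38.06 h3 and h2 = 1.71 h3; at 65% these are 0.1397, 0.0063 and 0.0037 per week.
- Expected enrolment of 5, 15, 25, 30, 40, 40, 30 per month (30.3.3); exponential withdrawal at 12% per year for effectiveness (30.3.4).
- Final analysis: Beta(1,1) prior and cut-off 0.9775 (30.2.1), leaving out failure-free subjects with incomplete follow-up (18.9.7).
- Safety success probability 0.858 (my value; Table 5 of Appendix D gives 0.860 at 7% and 65%).

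**1. Monte Carlo error at the cut-off.** SE = √(0.9975 × 0.0025 / 10,000) = 0.00050, and 0.0005 / 0.0025 = 20% of the tail. In counts, 25 ± 5 draws fall at or below 50%. The 95% band is 0.9975 ± 1.96 × 0.0005, or 0.9965 to 0.9985. Because the inequality is strict, early success needs at least 9,976 draws above 50%, so at most 24 below.

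**2. One case.** Suppose the exact probability is 0.9980. The expected count below 50% is 20, with SD √(10,000 × 0.002 × 0.998) = 4.47. By normal approximation the chance of at most 24 is Φ((24.5 − 20)/4.47) = Φ(1.01), about 0.84. Two seeds then disagree with probability 2 × 0.84 × 0.16, about 0.27.

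**3. The exact quantity.** The failure-free rate is exp(−[2h1 + 6h2 + 31h3]), so it exceeds 0.50 exactly when 2h1 + 6h2 + 31h3 < ln 2. With d failures and T weeks of exposure in a segment, the hazard's posterior is Gamma(1 + d, 1 + T), independent across segments. I computed this probability by 40 × 40 Gauss–Hermite quadrature. As a check on one data set, quadrature and 20 million draws both gave 0.99893.

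**4. The plan's own figure.** As written, my simulation gives early success on both endpoints in 55% of trials against the stated 64.8%, and overall power of 79.4–80.6% against 81.7%. I did not reproduce the 64.8%. The simulation details are incomplete: section 30.3.1, for example, mentions 2500 imputations for a predictive probability that the decision rule does not use. I therefore do not treat the mismatch as an error in the plan. Varying dropout start and rate, prior weight, prior time unit, enrolment process and look time gives 55–70%. A Gamma(0.5, 0.5) prior with 6% dropout comes close, at 64.0%.

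**5. Seed dependence.** For each simulated interim with exact probability P, let q = Pr(Binomial(10,000, P) ≥ 9,976). Two seeds disagree with probability 2q(1 − q). One run differs from the exact decision with probability 1 − q if P > 0.9975, and q otherwise. Averages over 8,000 trials per row, plan as written:

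| True failure-free rate | Two seeds disagree (effectiveness criterion) | One run differs from exact | Overall success changes with the seed |
|---|---|---|---|
| 50% | 0.01% | 0.007% | 0.005% |
| 55% | 0.4% | 0.3% | 0.08% |
| 60% | 2.1% | 1.5% | 0.14% |
| 62% | 2.9% | 2.0% | 0.10% |
| 65% | 2.9% | 2.1% | 0.06% |
| 70% | 0.9% | 0.6% | 0.001% |

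Requiring safety success as well, the 65% figure becomes 0.0291 × 0.858 = 0.025.

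**6. Sensitivity.** Across all the variants in step 4, two-seed disagreement stays at 1.9–3.2% for true rates of 60–65%. In the Gamma(0.5, 0.5) variant it is 2.6% at 65% and 2.5% at 60%. Fast and slow enrolment give 2.8% and 2.9% at 65%. The result does not hinge on the mismatch in step 4.

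**7. More draws, at a true 65%.**

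| Draws | SE at 0.9975 | Two seeds disagree |
|---|---|---|
| 10,000 | 0.00050 | 2.8–2.9% |
| 100,000 | 0.00016 | 0.8% |
| 1,000,000 | 0.00005 | 0.27% |
| Numerical integration | none | 0 |

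**The case against.** The sponsor has a good reply on most of the consequences.

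- **Missing early success is not failure.** The trial goes on to the final analysis, where borderline interims nearly always pass. A reader might infer from the 64.8% early-success share that the seed decides whether the trial succeeds. The documents do not support that: the route through the final analysis in section 30.2.1 remains open, and the last column of the first table shows how rarely the overall result moves. This stands.
- **Type I error.** A reader might infer that a noisy cut-off inflates it. It does not. Section 30.3 says the virtual trials applied the pre-specified interim rule, so on a plain reading the sampling noise is already inside the reported maximum of 0.023 (section 30.4.1). My own disagreement at the 50% null is about 0.01%. This stands.
- **Only one run is planned.** Section 18.8 gives the interim to an independent statistician. The figure for a single run is its departure from the exact decision, which is the smaller one. The two-run figure measures whether a re-run would confirm the result. Both are fair if labelled.
- **A seed may be fixed in the Main-study SAP.** I cannot exclude that. It would make the answer repeatable, but a borderline decision would still rest on an arbitrary number.
- **The evidence is strong either way.** In the affected trials the exact posterior probability lies roughly between 0.9965 and 0.9985. That is true, but the plan sets a sharp threshold and attaches consequences to it.

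A reader might also cite the share of interims in which the seed could matter. That depends on the definition. At 65% it is about 8.5% if the pass probability must lie between 5% and 95%, and about 12% for 1% to 99%. The wider band counts interims where one seed in a hundred would differ, so I rest on the disagreement rates instead.

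**Conclusion.** The point holds as a minor one about computation. Near the design assumption (a true failure-free rate of 60–65%) the interim effectiveness criterion is seed-dependent at the 2–3% level between two runs, and at 1.5–2% for one run against the exact answer. Away from that range the effect fades. It is no threat to type I error, and it moves overall success in about 0.1% of trials as written (at most 0.7% in any variant I tried). What is at stake is the six-month timing of the claim and whether the 12-month effectiveness result is inferential or descriptive.

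These sizes rest on the plan's hazard pattern, enrolment and withdrawal assumptions, on exposure counted in weeks, and on the rule as section 30.2.3 states it. They do not rest on the stated 64.8%.

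**What to change.** In Protocol section 30.2.3, replace the 10,000-draw step with numerical integration of Pr(2h1 + 6h2 + 31h3 < ln 2) over the three gamma posteriors. This is the preferred option, because the decision then depends on the data alone.

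Failing that, specify at least 1,000,000 draws and a fixed seed. This still leaves about 0.3% disagreement between seeds, so the seed must be written down before the interim.

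Either is a one-line edit and seconds of computing time. The model, prior, threshold and sample size stay unchanged. If the Main-study SAP describes the same step, it should carry the same wording.

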# **30.3** Simulation Scenarios

The operating characteristics of this trial were determined through trial simulation. We hypothesized several scenarios for the underlying rates for the effectiveness and safety endpoints and simulated the entire trial multiple times under each scenario. In each virtual trial, the interim analysis was conducted according to the pre-specified rules, and results were tracked for each trial, including whether the trial was successful on each endpoint individually and on both endpoints, whether trial success was achieved early, etc. This section describes the parameters that were used to simulate subject-level data for the virtual trials.

# **30.3.1** Effectiveness Profiles

In order to simulate the effectiveness outcome for a virtual subject, we need to simulate whether the subject has a failure and when that failure occurs. As previously discussed in section 29.2.3, a piecewise exponential time-to-failure model is assumed and calibrated to

	Biosense Webster, Inc	
Version 5.0 – Feb 3, 2021	CONFIDENTIAL	Page 129 of 135

have a particular failure rate  $(1 - p_E)$  at the end of follow-up. The profiles are constructed by taking advantage of the relationship:

$$p_E = \exp(-[2h_1 + (8-2)h_2 + (39-8)h_3]),$$

where  $p_E$  is the failure-free rate at 12-months. Previous study of catheter is assumed to estimate the hazard rates for the three pieces. From ThermoCool SSED, the reported hazard rates have the following pattern:

$$h_1 = (38.06)h_3; h_2 = (1.71)h_3; h_3 = (1)h_3.$$

To simulate data, we use the above multiplicative factors from ThermoCool and then find a value for  $h_3$ , such that when multiplied by each of the assumed rates for the three-time intervals, the failure-free rate at 12 months (39 weeks following 13weeks blanking period) matches the desired scenarios. Table 1 shows the derived hazard rates that were used to simulate data for a range of assumed failure-free rates.

	Hazard Rate (h)					
Failure-free Rate	$h_1$	$h_2$	$h_3$			
0.50	0.2248	0.0101	0.0059			
0.55	0.1938	0.0087	0.0051			
0.60	0.1656	0.0074	0.0044			
0.65	0.1397	0.0063	0.0037			
0.70	0.1157	0.0052	0.0030			
0.99	0.0032	0.0001	0.0001			

 Table 1: Parameters to generate failure times

In order to compute the predictive probability of success for the effectiveness endpoint, 2500 imputations were performed for each subject with missing outcome in the simulations

### 30.3.2 Adverse Event Rate Profiles

The 7-day PAE outcome for each subject is simulated as a Bernoulli random variable, with scenarios defined by the rates shown in Table 2.

 Table 2: Parameters to generate PAE outcomes

Version 5.0 – Feb 3, 2021

0.08	
0.10	
0.12	
0.14	

# 30.3.3 Enrollment Rates

We simulate three scenarios for the enrollment rate. The "expected" scenario assumes that full enrollment of N=185 would take approximately 7 months on average. The "fast" and "slow" scenarios assume that full enrollment would take, on average, 6 and 8 months respectively. Table 3 shows the rates for each scenario.

				Mo	onth			
Rate(patients/month)	1	2	3	4	5	6	7	8
Expected	5	15	25	30	40	40	30	
Fast	5	20	35	45	45	35		
Slow	2	10	20	30	35	35	35	18

### Table 3: Monthly enrollment rates

# **30.3.4** Attrition Rate Profile

For each subject, a time-to-withdrawal is simulated from an exponential distribution with a 5% dropout rate for the safety outcome and a 12% dropout rate for the effectiveness outcome. Both dropout rates are per year of follow-up. If a subject experiences a failure prior to their withdrawal time, then their outcome is recorded as a failure. A subject is censored at the time of withdrawal if the simulated withdrawal time is prior to the simulated failure time.

# **30.4 Operating Characteristics**

For the scenarios described above, we simulate multiple virtual trials and track the behavior of each trial, including the final outcome of the trial, whether success was declared early, etc. The results for Type I Error are based on 10,000 simulated virtual trials per scenario. For all other scenarios, 5,000 virtual trials were simulated.

# 30.4.1 Type I Error Control

This section summarizes the probability of a successful trial under the null hypotheses for both safety and effectiveness. Table 4 summarizes Type I error rates for the trial under various scenarios; that is, the probability of declaring success on both endpoints under two scenarios: (1) Assuming the true failure-free rate is 50% with various range of the true PAE rates; and (2) Assuming the true PAE rate is 14% with various range of the true failure-free rates.

	Biosense Webster, Inc	
Version 5.0 – Feb 3, 2021	CONFIDENTIAL	Page 131 of 135

The scenario that is expected to have the largest Type I error rate is either when the true PAE rate is 14% and the device is assumed to be effective (true failure-free rate is 99%), or when the true failure-free rate is 50% and the device is assumed to be safe (true PAE rate is 1%). The table shows the largest Type I error rate for the trial in the simulations was 0.023, still below the 2.5% threshold.

In adaptive trials, the enrollment rate to the trial directly impacts the amount of information that is available at the time of the interim and may influence the probability of stopping at the interim. In this simulation, however, there is little to no impact of different enrollment rates on Type I error, and notably, all values are below 2.5%.

	Pr(Declaring Success)						
Failure-free							
Rate	PAE Rate	Expected	Fast	Slow			
0.50	0.01	0.011	0.007	0.010			
0.50	0.07	0.008	0.009	0.007			
0.50	0.08	0.007	0.007	0.006			
0.50	0.10	0.004	0.005	0.004			
0.50	0.12	0.001	0.001	0.001			
0.50	0.14	0.000	0.000	0.000			
0.55	0.14	0.003	0.004	0.003			
0.60	0.14	0.012	0.013	0.012			
0.65	0.14	0.019	0.021	0.019			
0.70	0.14	0.021	0.021	0.020			
0.99	0.14	0.023	0.021	0.023			

# **30.4.2 Probability of Success**

For the full range of effectiveness and safety scenarios, this section summarizes the probability of trial success for the expected enrollment rate. Table 5 summarizes the probability of success in the following ways:

- **Both**: the proportion of virtual trials that were successful (on both endpoints) either at an interim or at the final analysis
- Effectiveness: the proportion of trials that were successful on the effectiveness endpoint
- Safety: the proportion of trials that were successful on the safety endpoint

- **Early**: the proportion of trials that met the criteria for success (on both endpoints) at the interim analysis
- **Final**: the proportion of trials that met the criteria for success (on both endpoints) at the final analysis when the early success is not declared.

If the true PAE rate is 7% and the true failure-free rate is 65%, the trial has approximately 81.7% power. Under this scenario, 64.8% of the simulated trials claimed success at the interim and an additional 16.9% of trials achieved success at the final analysis. *Table 5: Pr(Declaring Success) (Expected Enrollment)* 

Failure-free	Pr(Declaring Success)					
Rate	PAE Rate	Both	Effectiveness	Safety	Early	Final
0.50	0.07	0.008	0.010	0.856	0.002	0.007
	0.08	0.007	0.010	0.696	0.001	0.006
	0.1	0.004	0.009	0.342	0.001	0.003
	0.12	0.001	0.010	0.105	0.000	0.001
	0.14	0.000	0.009	0.021	0.000	0.000
0.55	0.07	0.144	0.169	0.853	0.046	0.098
	0.08	0.114	0.161	0.710	0.035	0.079
	0.1	0.058	0.160	0.352	0.018	0.040
	0.12	0.016	0.148	0.101	0.006	0.010
	0.14	0.003	0.153	0.020	0.001	0.002
0.60	0.07	0.530	0.625	0.847	0.270	0.261
	0.08	0.439	0.613	0.705	0.225	0.214
	0.1	0.209	0.613	0.340	0.104	0.105
	0.12	0.063	0.625	0.104	0.030	0.033
	0.14	0.012	0.617	0.021	0.006	0.006
0.65	0.07	0.817	0.952	0.860	0.648	0.169
	0.08	0.661	0.953	0.696	0.522	0.138
	0.1	0.325	0.951	0.338	0.260	0.064
	0.12	0.099	0.954	0.104	0.078	0.021
	0.14	0.019	0.948	0.021	0.015	0.004
0.70	0.07	0.852	0.999	0.853	0.824	0.028
	0.08	0.699	0.999	0.700	0.680	0.019
	0.1	0.347	0.998	0.347	0.336	0.011
	0.12	0.107	0.999	0.107	0.104	0.003
	0.14	0.021	0.999	0.021	0.020	0.001

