## **18.7** Sample Size Justification

#### The Main study:

The Final analyses for primary safety and effectiveness endpoints will apply Bayesian methods and use a beta-binomial model after all subjects complete the 12 months

Biosense Webster, Inc

Version 5.0 – Feb 3, 2021 CONFIDENTIAL

follow-up (assuming early success is not achieved for the primary effectiveness endpoint). Non-informative Beta priors will be used for both safety and effectiveness endpoints. Trial simulations were performed to estimate the power for the success of the safety and effectiveness endpoints. Based on PG of 14% for the primary safety endpoint and PG of 50% for the primary effectiveness endpoint, the sample size of 185 subjects will provide above 80% power to declare success for both endpoints controlling the overall type-I error rate at one-sided 2.5% assuming the true PAE rate is 7% and the true effectiveness failure-free rate is 65%. It is also assumed that there are 5% and 12% dropout rates for the safety and effectiveness endpoints, respectively.

Simulations were also performed to estimate the overall type I error for this study under various hypothetical scenarios. The highest type I error rates were reached in the following two scenarios, including 1) the true primary safety rate was on the decision boundary (i.e. equal to 14%) and the device was assumed to be effective: type I error rate was 0.023, and 2) the true primary effectiveness rate was on the decision boundary (i.e. equal to 50%) and the devices was assumed to be safe: type I error rate was 0.011. As the primary safety or effectiveness moves away from the decision boundary, the overall Type-I error decreases. Therefore, considering all scenarios, the overall type I error for claiming success for both safety and effectiveness was controlled at 2.5%.

Based on the simulation results, the study is adequately powered to meet the primary safety and effectiveness endpoints and Type-I error for the overall trial success is controlled at 2.5%.

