# 18.9.7 Handling of Missing Data

Missing data will be queried for reasons and handled on an individual basis.

At the time of early success interim analysis in the Main study (final safety analysis), if a subject's safety follow-up data is missing but a PAE has occurred earlier, then the subject will be considered having an event. If a subject's follow-up data is missing for the 3-month follow-up and the subject has not had a PAE, then that subject will be excluded from the early success safety analysis. For each early success interim analysis of the effectiveness endpoint, the subjects with incomplete follow-up data will be censored at the time of their last follow-up visit, and only their observed partial follow-up time will contribute to estimating model parameters.

For the variable flow study, if a subject is missing 3-month follow-up and the subject has not had a PAE, the subject will be excluded from the primary safety endpoint analysis. Information will not be borrowed from subjects in the Main Study without PAE but were missing 3-month follow-up.

For final effectiveness analysis in the Main Study, if a subject has an effectiveness failure at any time during the evaluation period, then the subject will be considered having an event. Subjects without an effectiveness failure who do not have full 12 months of followup will be excluded from the final effectiveness analysis.

For the primary effectiveness endpoint analysis in the variable flow study, if a subject has an effectiveness failure at any time during the evaluation period, then the subject will be considered having an event. Subjects without an effectiveness failure who do not have full 12 months of follow-up will be excluded from the final effectiveness analysis. No information will borrowed from subjects who are failure free in the Main study but do not have full 12-month follow-up.

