### 30.1.1.2 Primary Safety Endpoint

The primary safety endpoint is occurrence of primary adverse events(PAE) within 7 days of an ablation procedure. The PAE rate will be compared against a PG of 14%. PAE includes the following AEs and are defined in the protocol:

- Death
- Atrio-Esophageal Fistula
- Cardiac Tamponade/Perforation
- Myocardial Infarction
- Stroke / Cerebrovascular Accident
- Thromboembolism
- Transient Ischemic Attack
- Diaphragmatic Paralysis
- Pulmonary Vein Stenosis
- Pericarditis
- Vagal Nerve Injury
- Major Vascular Access Complication / Bleeding

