### 30.2 Adaptive Design

### **30.2.1** Primary Analysis

The primary goal of the trial is to demonstrate effectiveness and safety. For the trial to be successful, both primary safety and effectiveness endpoints must be statistically significant relative to their respective PGs.

The effectiveness endpoint will be assessed by testing the hypotheses (assuming early success for effectiveness is not achieved):

	Biosense Webster, Inc	
Version 5.0 – Feb 3, 2021	CONFIDENTIAL	Page 127 of 135

$$H_0: p_E \le 0.50$$
 vs.  $H_A: p_E > 0.50$ ,

where  $p_E$  is the proportion of patients free from effectiveness events.

Let X be the number of patients that are failure-free through 12 months. We model the number of patients free from an event as

$$X \sim \text{Binomial}(n, p_E),$$

where *n* is the number of patients. We use a vague Beta(1, 1) prior distribution for  $p_E$ . Then the posterior distribution is

$$(p_E|x,n) \sim \text{Beta}(1+x,1+n-x).$$

Similarly, the hypothesis test for the safety endpoint is:

$$H_0: p_S \ge 0.14$$
 vs.  $H_A: p_S < 0.14$ ,

where  $p_S$  is the 7-day PAE. We model the number of patients with PAEs as

$$Y \sim \text{Binomial}(n, p_S)$$

with a vague Beta(1, 1) prior distribution on  $p_s$ .

Assuming early success for effectiveness is not achieved, the trial will be considered a success if BOTH

- 1.  $\Pr(p_E > 0.5 | x, n) > 0.9775$  AND
- 2.  $\Pr(p_S < 0.14 | y, n) > 0.975.$

These thresholds control the overall Type I error rate for the trial below one-sided 2.5% (see Section 29.5.1 of this report for additional discussion of Type I error control).

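### The Main-study joint power of 81.7% does not reproduce under the written missing-data rules, which give about 78-79% and at most about 80% under more favourable readings

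*Protocol*

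**What the plan says.** Protocol Appendix D (30.1): "The trial will enroll N=185 subjects". Section 30.4.2 reports for the planning scenario that "the trial has approximately 81.7% power", split as 64.8% early and 16.9% at the final analysis. Table 5 gives 0.952 for effectiveness alone and 0.860 for safety alone. Section 30.4.3 says joint power is about 81.7% at every enrolment speed. Section 18.7 turns this into the sample-size claim: "the sample size of 185 subjects will provide above 80% power to declare success for both endpoints", with 5% and 12% dropout.

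The missing-data rules are in two places. Under 18.9.7, a subject who fails at any time in the evaluation period counts as a failure, while subjects without a failure who "do not have full 12 months of followup will be excluded from the final effectiveness analysis". Section 30.3.4 has the same asymmetry in the simulation: a failure before withdrawal is recorded as a failure, and otherwise the subject is censored at withdrawal. Dropout for effectiveness is exponential at 12% per year. For safety, 18.9.7 keeps a PAE that occurred before loss and excludes PAE-free subjects with no 3-month follow-up.

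**The concern.** Keeping the failures of people who later leave, while deleting the people who leave without failing, lowers the analysed success rate below the true rate. A simulation that applies this rule should show the cost in power. The tabled effectiveness power of 95.2% is higher than the rule allows. At stake is the claim that 185 subjects give more than 80% power for both endpoints together, which is the whole sample-size justification for the Main study.

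**Working it through.** **Inputs (all Protocol).** N = 185 (30.1). Hazard ratios 38.06 : 1.71 : 1 over weeks 0-2, 2-8 and 8-39 after blanking (30.3.1). Expected enrolment 5, 15, 25, 30, 40, 40, 30 per month (Table 3). Interim 6 months after the last enrolment, Gamma(1,1) prior on each hazard, threshold 0.9975 (30.2.2, 30.2.3). Final Beta(1,1)-binomial, thresholds 0.9775 for effectiveness and 0.975 for safety (30.2.1). Dropout 12% and 5% per year (30.3.4). The start of the dropout clock is not stated, so both options are shown: from the procedure, or from the end of blanking.

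**1. The plan's own figure.** 64.8% + 16.9% = 81.7%. The product of the tabled marginals, 0.952 × 0.860 = 0.819, agrees. The tables are therefore internally consistent, and joint power can be taken as a product.

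**2. Analysed success rate at a true 65%.**
- Weekly dropout hazard k = −ln(0.88)/52 = 0.002458.
- Completes failure-free: 0.65 × 0.88^(39/52) = 0.65 × 0.9086 = 0.5906.
- Failure seen before withdrawal: ∫ f(t)·exp(−kt) dt = 0.2432 + 0.0276 + 0.0740 = 0.3448 over the three segments.
- Analysed rate = 0.5906 / (0.5906 + 0.3448) = 63.1%.
- Expected n = 185 × 0.9354 = 173 with the clock from the end of blanking. With the clock from the procedure both terms are multiplied by 0.88^(13/52) = 0.9685, so n is about 168 and the rate is unchanged.

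**3. Effectiveness power.** At n = 173 the final test needs 100 successes. The chance of that is 97.9% at a rate of 65% and 93.6% at 63.1%. Averaging exactly over the random n gives final-analysis power of 92.4% (procedure clock) or 93.2% (end-of-blanking clock). Simulating the whole design with the Gamma(1,1) interim (15,000 trials per reading) gives 92.7% or 93.4%. Stated: 95.2%.

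**4. Safety power.** At n = 180-185 up to 16 PAEs are allowed. Dropout before 3 months is 1 − 0.95^0.25 = 1.27%. Keeping early PAEs of dropouts, as 18.9.7 requires, gives 84.5%. Discarding them gives 85.6%. Stated: 86.0%, so safety explains little of the gap.

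**5. Joint power** (effectiveness × safety):

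| Interim prior, dropout clock | Effectiveness | × 0.845 (PAEs kept) | × 0.856 (PAEs discarded) |
|---|---|---|---|
| Gamma(1,1), procedure | 92.7% | 78.4% | 79.4% |
| Gamma(1,1), end of blanking | 93.4% | 78.9% | 80.0% |
| Near-flat, procedure | 93.3% | 78.9% | 79.9% |
| Near-flat, end of blanking | 94.0% | 79.5% | 80.5% |

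The first two rows with PAEs kept are the rules as written. Safety attrition read as a flat 5% with the Gamma(1,1) prior lowers joint power to 77.1% or 77.7%.

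**6. Other rows.** At a true rate of 0.60 the analysed rate is 58.0% and effectiveness power is 0.53-0.57. The 15 tabled cells run from 0.609 to 0.632. At 0.55 the recomputed power is 0.10-0.12, against 0.144-0.169 tabled. With 5,000 trials per cell, the Monte Carlo standard error at 0.62 is √(0.62 × 0.38 / 5000) = 0.7 points, so noise does not explain the gap.

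**7. What would fit.** The tabled effectiveness profile matches roughly 6-7% attrition over the 39 weeks. The stated 12% per year implies 1 − 0.88^0.75 = 9.1%.

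**The case against.** The best case for the protocol has four parts.

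- **The interim prior.** The stated early success of 64.8% implies about 0.648 / 0.860 = 75% early success on effectiveness alone. Gamma(1,1) gives 64-67% and a near-flat prior 79-80%, so the reported simulation looks closer to a near-flat prior.
- **Safety.** The 15 tabled safety powers at a 7% PAE rate average 0.857, which fits discarding early PAEs of dropouts (0.856) better than keeping them (0.845). Combined with a near-flat prior, joint power is 79.9-80.5%, and the gap to 81.7% falls to 1.2-1.8 points.
- **Incomplete specification.** The start of the dropout clock is missing. Section 30.3.1 mentions 2,500 imputations per missing outcome and a predictive probability that no decision rule uses. The simulation code is not in the documents, nor is the separate Main-study SAP that the protocol refers to.
- **Simpler calculations.** With fixed evaluable numbers of 163 and 176, joint power is 0.9687 × 0.828 = 80.2%. Excluding every non-completer, failures included, gives 80.3-83.0%.

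Much of this stands. A reader might infer that joint power is below 80% on any reading, and the documents do not support that. But each route to 80% or more departs from the text: it replaces the stated prior, discards PAEs that 18.9.7 keeps, or drops the asymmetric exclusion rule. Excluding all non-completers also gives an effectiveness type I error of about 0.02-0.025, against 0.008-0.010 in the tables, so it is not what the report ran. Even with the protocol's own safety power, the Gamma(1,1) readings give 0.927 × 0.860 = 79.7% or 0.934 × 0.860 = 80.3%, not 81.7%.

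**Conclusion.** The concern holds in a limited form. Under the written rules, effectiveness power at a true 65% is about 93% rather than 95.2%, and joint power is about 78-79% rather than 81.7%, a shortfall of roughly 3 points. More favourable readings bring it to about 80%. The overstatement is larger at a true rate of 0.60, at 4-10 points on effectiveness.

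This rests on independent endpoints (as the tabled marginals imply), the Gamma(1,1) prior in weekly units (as in Table 1 of Appendix D), and either start of the dropout clock. The cause cannot be confirmed without the code.

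A reader might also infer that type I error control fails or that an individual endpoint is underpowered. Neither follows. The exclusion rule pushes the analysed rate down, so it makes the effectiveness test more conservative, and power for each endpoint taken alone stays above 80% under the written rules.

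**What to change.** Re-run the Appendix D simulation with the Gamma(1,1) prior, the 5% and 12% annual dropout rates and the 18.9.7 missing-data rules as written. State when the dropout clock starts, and either explain the imputation sentence in 30.3.1 or remove it. Then restate joint and effectiveness power in 18.7, 30.4.2 and 30.4.3 and in Tables 5-7. The expected joint power is about 78-80%, but the replacement figure should come from the re-run. Remove the above-80% wording if the re-run does not support it. If different rules were in fact simulated, state them and reconcile them with 18.9.7.

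The cost is one re-run and probably a slightly less favourable figure. No decision threshold has to change.
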